- Signs of active infection on CXR
- Positive interferon gamma release assay Quantiferon or T.Spot TB test: must be treated with at least 4 weeks post initiation of isoniazid or other TB therapy
- Inherited or acquired severe immunodeficiency
- History of malignancy
- Patient with active severe infection (excluding fungal infections of the nail), which has required antibiotic treatment within 2 week prior to study enrolment
- Infection requiring hospitalisation or intravenous antibiotic treatment within the last 8 weeks prior to enrolment

- Past history of osteomyelitis, or fasciitis, septic arthritis within the last one year
- Patients with drug induced pemphigus. A thorough medication history will be taken to rule out drug induced pemphigus including D-penicillamine, angiotensin-converting enzyme inhibitors, angiotensin receptor blockers and cephalosporins
- Evidence of any new or uncontrolled concomitant disease that in the investigators' judgement would preclude the patients participation
- Patients with history of allergy or adverse events to IVIG or rituximab treatment¹⁰
- Treatment with intravenous immunoglobulins, plasmaphoresis within the last 8 weeks prior to randomization
- Previous treatment with rituximab or any monoclonal antibody inducing profound lymphopenia
- Treatment with live or attenuated vaccine within the last 28 days prior to randomization

Admission and follow up:

- All infusions will be performed as in-patient procedure of prospective hospital and all patients are to be follow up monthly at out-patient of the prospective Queen Mary Hospital dermatology out-patient clinic
- Patients will be followed up monthly for the first 6 months, then followed up for every 3 months up to 4 years starting from baseline visit

Outcome measures:

Patients' serum will also be taken for desmoglein antibodies and levels will be charted and independent samples t-test will be used to compare the collected data between the two groups. Homogeneity of the treatment groups at baseline will be analyzed using the Mann–Whitney U test and Wilcoxon signed-rank test for independent and dependent variables. The Kaplan-Meier method will be used to estimate the likelihood of reaching the endpoint of relapses or flares within the drug infusing period based on the intention-to-treat population, defined as all patients who has received at least one dose of study medication. The log-rank test will be used to compare time-to-event curves between treatment groups.

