Statistical analysis of results will be done with IBM SPSS statistic program version 25. All tests of significance are two-tailed, and a P value of < 0.05 is considered to indicate statistical significance.

Primary outcome:

- 1) Percentage of participants who achieve relapse-free complete remission

Secondary Outcomes:

- 2) Time to protocol defined disease flare
- 3) Duration of complete remission, evaluated by the PDAI activity score [Baseline up to end of study]
- 4) Number of protocol defined disease flares
- 5) Time to initial complete remission, evaluated by the PDAI activity score [Baseline up to end of study]
- 6) Change in health-related quality of life as measured by the Dermatology Life Quality Index (DLQI) Score [Time Frame: Baseline, Week 4, 12, 24, 36, 48, 60, 72, 84, 96, 120, 144, 168, 192]
- 7) Occurrence of severe treatment adverse events (grade 3 or 4) based on common terminology criteria for adverse events (CTCAE), or death from any cause
- 8) Blood DSG 1 and 3 levels [Baseline week 0, week 4, 12, 20, 24, 36, 48, 60, 72, 96, 120, 144, 168, 192]
- 9) Blood lymphocyte level (CBC) [Baseline week 0, week 4, 12, 24, 36, 48, 60, 72, 96, 120, 144, 168, 192]
- 10) Blood CD19/20 mean B cell counts percentage [Time Frame: Baseline, week 4, 12, 20, 24, 36, 48, 60, 72, 96, 120, 144, 168, 180, 192]
- 11) Number of rescue therapy given

Baseline investigations prior to commencing therapy

General investigations:

- CBC
- Renal panel
- Liver panel
- Fasting Glucose/HbA1c
- Urine microscopy
- Urine pregnancy test in women of childbearing age
- Serum immunoglobulins for IgA deficiency
- B cell (CD19/20) enumeration

- DSG 1, 3 ELISA

Infective screen:

- HepBs Ag, Anti-HBs Ab, anti-HepBc total antibodies
- Anti-HCV IgG
- Anti HIV 1 and 2 (if indicated)
- CXR
- Interferon-gamma release assays

Patients who have positive IGRA test results

As Tuberculosis (TB) is endemic in Southeast Asia, should Interferon-gamma release assays result be positive, the patient will be reviewed by infectious diseases specialist and need treatment of latent TB treatment prior to starting Rituximab. Patients will need to have completed at least 4 weeks of isoniazid or treatment with other TB medications, before commencement of the study.

Patients who are HepBs Ag positive, or HepBs Ag negative and anti-HepBc Ab – positive

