Viral hepatitis is a major healthcare burden especially in Hong Kong, which is considered to be part of an endemic region. The seroprevalence of anti-HepBc is estimated to be as high as 37.3%,¹¹ therefore the exclusion of HepBs Ag positive and HepBc Ab positive patients were amended in study protocol, and these patients will be included in the study.

Baseline HepB DNA levels will be done for patients who are HepBs Ag positive, and anti-hepBc Ab positive

Patients will be monitored for AST and ALT levels at least every 3 months, HepBsAg and HBV DNA tests repeated whenever clinically indicated

Patients who are HepBs Ag positive – will be started on entecavir 0.5mg daily, and will be referred to a gastroenterologist for further follow up.

Patients who are HepBs Ag negative, and HBc Ab positive, with detectable HepB DNA levels – will be started on entecavir 0.5mg daily, and will be referred to a gastroenterologist for further follow up.

Patients who are HepBs Ag negative, HBc Ab positive, with no detectable HepB DNA levels, will be started on entecavir 0.5mg daily, and will be continued on entecavir for at least 18 months after completion of last dose of rituximab.^{12,13}

Monitoring and definitions of disease outcome parameters:¹⁴

- **Control of disease activity:** Time at which new lesions cease to form and established lesions begin to heal.
- **End of consolidation phase:** Time at which no new lesions have developed for a minimum of 2 weeks and approximately 80% of lesions have healed
- **Complete remission:** The absence of new or established lesions
- **Complete remission off therapy:** The absence of new or established lesions while the patient is off all systemic therapy for at least two months.
- **Relapse/flare:** Appearance of ≥ 3 new lesions/month that do not heal spontaneously within 1 week, or by the extension of established lesions, in a patient who has achieved disease control

Steroid regimen and tapering:

Prednisolone tapering³

Severe Pemphigus (PDAI ≥ 45):⁹

- Prednisolone 1mg/kg/day for 1 month, then 0.75mg/kg/day for 1 month then 0.5mg/kg/day for 1 month, then 0.3mg/kg/day for 1 month then 0.2mg/kg/day for 1 month, then 0.1mg/kg/day for 1 month then off

Moderate pemphigus (PDAI ≥ 15):⁹

- Prednisolone 0.5mg/kg/day for 1 month, then 0.3mg/kg/day for 1 month then 0.2mg/kg/day for 1 month then off

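### Flare can occur only after disease control but is analysed in all treated patients, so the flare comparison can favour the arm with poorer or slower control; the primary outcome is not affected

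*Protocol*

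**What the plan says.** Protocol, *Monitoring and definitions of disease outcome parameters*, sets two linked definitions. Disease control is "Time at which new lesions cease to form and established lesions begin to heal". Relapse/flare is either a minimum number of new, non-healing lesions in a month, "or by the extension of established lesions, in a patient who has achieved disease control".

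Protocol, *Outcome measures*, then fixes how the event is analysed. On the estimator it says: "The Kaplan-Meier method will be used to estimate the likelihood of reaching the endpoint of relapses or flares within the drug infusing period". The same sentence goes on to name the analysis set, with no condition on disease control: "based on the intention-to-treat population, defined as all patients who has received at least one dose of study medication". For the comparison between arms it adds: "The log-rank test will be used to compare time-to-event curves between treatment groups".

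Protocol, *Secondary Outcomes*, lists outcome 2, "Time to protocol defined disease flare", and outcome 4, "Number of protocol defined disease flares". The primary outcome is the percentage with relapse-free complete remission.

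Protocol, *Relapse/ failure to achieve complete remission*, names relapse and failure to remit as two separate triggers for further rituximab. Non-response is therefore not itself a flare.

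**The concern.** The event and the population do not fit together. A patient must reach control before a flare is possible, but the analysis set includes patients who have not reached control and may never do so. The Protocol gives no time origin at control, no restriction of the risk set to controlled patients, and no rule that treats failure to reach control as an event or a competing event.

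Under an ordinary Kaplan-Meier analysis from baseline this has two consequences:

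- A patient who is never controlled cannot have the event and stays on the curve as flare-free, even if given further rituximab for failure to remit.
- A patient controlled late enters risk late and has less time to flare before the infusion period ends.

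Both work in the same direction. An arm that controls more patients, or controls them sooner, exposes more patient-time to flare. The log-rank test could then point towards the less effective arm.

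**Working it through.** **Plan's own figure.** There is none to reproduce on this point. The Protocol gives about 10 patients per arm (*Methods*) with no control rate, flare rate or power. All rates below are assumptions.

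**Step 1: flare-free proportion in all treated patients.** Let c be the proportion ever controlled and f the flare risk after control.

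- Analysis from baseline, never-controlled patients kept as flare-free: flare-free = 1 − c × f.
- Failure to reach control counted as an event: success = c × (1 − f).

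| Control, better vs weaker arm | Flare risk after control | Flare-free, 1 − cf | Controlled and flare-free, c(1 − f) |
|---|---|---|---|
| 90% vs 90% | 30% vs 30% | 73% vs 73% | 63% vs 63% |
| 95% vs 80% | 30% vs 30% | 71.5% vs 76% | 66.5% vs 56% |
| 90% vs 70% | 30% vs 30% | 73% vs 79% | 63% vs 49% |
| 90% vs 50% | 30% vs 30% | 73% vs 85% | 63% vs 35% |
| 90% vs 70% | 30% vs 40% | 73% vs 72% | 63% vs 42% |
| 90% vs 50% | 30% vs 40% | 73% vs 80% | 63% vs 30% |

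Example, third row: 1 − 0.90 × 0.30 = 0.73 and 1 − 0.70 × 0.30 = 0.79; then 0.90 × 0.70 = 0.63 and 0.70 × 0.70 = 0.49.

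**Step 2: when the direction reverses.** The weaker arm looks better when its flare risk, divided by that of the better arm, is below the ratio of control rates (better over weaker). For 90% vs 50% that ratio is 0.90/0.50 = 1.8. A flare-risk ratio of 0.40/0.30 = 1.33 is below it, so the order reverses. For 90% vs 70% it is 0.90/0.70 = 1.29, which 1.33 exceeds, so the order is right but the gap shrinks to one point.

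**Step 3: effect per patient.** With 10 per arm, one patient left uncontrolled instead of controlled raises the expected flare-free proportion by 10 points × f, that is 3 points at f = 30%. The table agrees: going from 9 to 5 controlled moves 73% to 85%, and 12/4 = 3.

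**Step 4: late control alone.** Take a 76-week window as an assumption; the Protocol's text and table give different end weeks for Arm 1 infusions. Assume a constant flare hazard after control giving 40% in 12 months (52 weeks).

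- Control at week 4 leaves 76 − 4 = 72 weeks at risk: flare-free 0.6^(72/52) = 49%.
- Control at week 30 leaves 76 − 30 = 46 weeks: flare-free 0.6^(46/52) = 64%.

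The slower patient looks better with the same underlying hazard.

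**Step 5: simulated log-rank test.** 10 per arm, 3,000 trials per setting, that same hazard in both arms, median 2 months to control in both arms, follow-up to 17.5 months (about 76 weeks), never-controlled patients censored without event.

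| Control, better vs weaker arm | Favours weaker arm | Significantly so | Favours better arm if non-response is an event |
|---|---|---|---|
| 90% vs 90% | 49% | 3% | 50% |
| 95% vs 70% | 70% | 7% | 79% |
| 90% vs 50% | 81% | 13% | 91% |

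The first row has no truly weaker arm and serves as the reference. The last column places non-response at time zero. It shows the direction of the correction, not the operating characteristics of a rule tied to a later visit.

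**The case against.** Several objections have weight.

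- **The Protocol does not say that uncontrolled patients are carried as event-free.** It names an estimator, a test and a population, and leaves time origin, entry to risk and censoring open. A separate SAP, not seen here, could settle these by delayed entry at control or a competing event. This stands as a limit: the distortion follows from the usual analysis, not from an explicit instruction. But the event and population are fixed in the Protocol, and they conflict.
- **Uncontrolled patients may be few.** The threshold for control is low, both arms receive rituximab with a prednisolone taper, and failure to remit leads to more rituximab. This stands and limits the likely size. Late control would still matter.
- **The definition could be parsed so that prior control qualifies only lesion extension.** This is weak: the comma and the word relapse point to both limbs. If the narrow reading was meant, the wording still needs repair.

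Some stronger readings are tempting but unsupported:

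- **A reader might infer that treatment failure is scored as success throughout the trial.** It is not. A never-responder fails the primary outcome, and time to initial complete remission (outcome 5) and rescue therapy (outcome 11) also reveal non-response.
- **A reader might infer that the bias must fall on the combination arm because its rituximab is front-loaded.** By week 8 the tables do give 8 doses in Arm 2 against 4 in Arm 1. But Arm 1 leads 4 to 3 at week 3, the arms tie at 4 in week 4, and Arm 2 leads only from week 5. The Protocol states no expected difference in speed of control, so the direction is unknown.
- **A reader might infer that each uncontrolled patient costs 10 points.** That holds only against a composite that counts the patient as a failure. Against the same patient being controlled, the shift is about 3 points at a 30% flare risk.
- **A reader might infer that outcome 4 carries the same stated fault.** The all-treated population is tied only to the Kaplan-Meier analysis. Outcome 4 has no stated denominator, so it needs context rather than correction.

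**Conclusion.** The point holds for the Kaplan-Meier/log-rank analysis of relapse or flare and for outcome 2. An event that requires prior control is analysed in patients who may never have reached it. A standard analysis from baseline can then favour the arm with poorer or slower control.

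At an assumed equal 30% flare risk after control, the weaker arm appears 6 points better when control is 90% vs 70% (79 − 73) and 12 points better at 90% vs 50% (85 − 73). There is no distortion when control is equal in frequency and timing. The true size cannot be derived from the Protocol. At about 10 per arm the more likely harm is a misleading direction than a false significant result: in the most extreme simulated setting the weaker arm was favoured in 81% of trials, significantly in 13%.

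This is a fault in a secondary analysis that should be corrected. It does not threaten the primary outcome.

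**What to change.** - **All-treated Kaplan-Meier/log-rank analysis and outcome 2.** Start at randomisation. Define the event as flare, or failure to reach disease control by one pre-specified existing visit common to both arms, with failures counted as events at that visit. Week 24, the last of the monthly visits, is one candidate.
- **Data collection.** Record the visit at which control is first met. The Protocol defines control but does not list it as an outcome or schedule a record of its date.
- **Descriptive result.** Report time from control to flare among controlled patients, with the proportion controlled in each arm beside it. This is not a randomised comparison.
- **Outcome 4.** Report the number of flares beside the number controlled and the patient-time after control.

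The cost is a wording change and one added data item at visits already planned. The event becomes a composite that partly overlaps the primary outcome, event-free figures will look less favourable, and a patient controlled after the chosen visit counts as a failure. The visit should therefore be fixed before any outcome data by arm are examined.

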Annex 1 Pemphigus disease area index (PDAI)

Skin	Activity	Damage
Anatomical location	Erosion/Blisters or new erythema	Post-inflammatory hyperpigmentation or erythema from resolving lesion
	0 absent 1 1–3 lesions, up to one >2 cm in any diameter, none > 6 cm 2 2–3 lesions, at least two > 2 cm diameter, none > 6cm 3 >3 lesions, none > 6 cm diameter 5 >3 lesions, and/or at least one >6 cm 10 >3 lesions, and/or at least one lesion >16 cm diameter or entire area	Number lesions if ≤ 3 0 absent 1 present
Ears		
Nose		
Rest of the face		
Neck		
Chest		
Abdomen		
Back, buttocks		
Arms		
Hands		
Legs		
Feet		
Genitals		
Total skin	/120	/12

Scalp	Activity	Damage
Scalp	Erosion/Blisters or new erythema	Post-inflammatory hyperpigmentation or erythema from resolving lesion
	0 absent 1 in one quadrant 2 two quadrants 3 three quadrants 4 affects whole skull 10 at least one lesion > 6 cm	Number lesions if ≤ 3 0 absent 1 present
Total Scalp (0–10)	/10	/1

Mucous membrane	Activity	Damage
Anatomical Location	Erosion/Blisters	Number lesions if ≤ 3
	0 absent 1 1 lesion 2 2–3 lesions 5 >3 lesions or 2 lesions >2 cm 10 entire area	
Eyes		
Nose		
Buccal mucosa		
Hard palate		
Soft palate		
Upper gingiva		
Lower gingiva		
Tongue		
Floor of mouth		
Labial bucosa		
Posterior pharynx		
Anogenital		
Total Mucosa	/120	

Total Activity Score:

Total Damage Score

Additional notes:

